5.1.2. Exclusion Criteria

Potential subjects meeting any of the following criteria will be excluded from participation in this study:

- 1. Patient showing signs of respiratory failure necessitating mechanical ventilation
- 2. Pregnant or nursing women.
 - NOTE: Women of child-bearing potential and men must agree to use adequate contraception (hormonal or barrier method of birth control; or abstinence) prior to study entry and for the duration of study participation. Should a man father a child, or a woman become pregnant or suspect she is pregnant while participating in this study, he or she should inform the treating physician immediately.
- 3. Active or uncontrolled infections other than COVID-19 or with serious illnesses or medical conditions which would not permit the patient to receive study treatment
- 4. Active or planned concomitant treatment with other investigational antivirals or immunomodulators
- 5. Chronic diarrhea (excess of 2-3 stools/day above normal frequency)
- 6. Current use or anticipated need for drugs that are known strong inhibitors or inducers of major CYP enzymes.

CONFIDENTIAL Page 28 of 66

5.2. SCREEN FAILURES

All subjects who fail to meet eligibility criteria are considered screen failures, and are exited from the study. Subject number, demographics and reason for screen failure will be recorded.

If a subject initially fails to meet inclusion/exclusion criteria and is later reconsidered for participation, the subject will be re-consented and assigned a new unique identification number at the time of re-screening and may be enrolled if they are found to meet all inclusion and no exclusion criteria at the subsequent screening visit.

CONFIDENTIAL Page 29 of 66

6. STUDY TREATMENT

6.1. STUDY TREATMENT ADMINISTRATION

6.1.1. Investigational Drug Product Description

For this study, the investigational product is CX-4945 that will be assigned to the subjects randomized to the treatment Arm A.

Refer to Investigator Brochure or summary of product characteristics.

All subjects enrolled in the study (Arm A and Arm B) may be treated with SOC/best supportive care as per the investigator's discretion and in accordance with the site standard clinical practice. The patients randomized to the treatment Arm A will receive SOC/best supportive care therapy in combination with CX-4945. The patients randomized to the control Arm B will receive SOC/best supportive care alone.

6.1.2. Randomization

Randomized treatment assignments for the subjects will be done after confirmation of subject's eligibility, and prior to any other Day 1 study assessments. Subjects will be allocated randomly into Arm A and Arm B in a 1:1 ratio.

Arm SOC/ Daily dose of Dose AM Dose PM Dose No. of **SUPPORTIVE** CX-4945 administration capsules/day (mg) (mg) **CARE** (mg) b.i.d. (mg) 1000 1000 Assigned by the 2000 1000 10 A investigator 0 0 0 0 0 В Assigned by the investigator

Table 2. Method of Assignment to Treatment

6.1.3. Dosing and Administration of CX-4945

Patients enrolled to the treatment Arm A will receive 1000 mg of CX-4945 twice daily by mouth, beginning on Day 1, and continuously through Day 14.

Patients will be instructed to take oral antiemetic prophylaxis at least 1 hour prior to taking the study drug. Other oral medications should be taken at least one hour before or 2 hours after ingesting the dose of CX-4945 capsules.

CONFIDENTIAL Page 30 of 66

^{*}SOC and Supportive Care are defined in Section 4.1.

Patients will take five 200-mg CX-4945 capsules twice daily, two hours after the morning meal and two hours after the evening meal (dinner) with water. Patients are advised to take 1 capsule at a time with a pause in between each. This method may prevent a clumping effected in the stomach, so patient can take as much as 10 minutes to swallow each capsule.

The study drug will be taken on an empty stomach with at least six ounces (180 mL) of water. After CX-4945 administration, the patient will be NPO (except for water) for 2 hours, after which, the patient may eat.

6.1.4. Investigational Product Compliance

Site staff will dispense Investigational Product (CX-4945) to the study subjects randomized to the Treatment Arm A. If a patient misses a dose, he or she should be instructed not to take or make up that dose and to resume dosing with the next scheduled dose. Missed doses will not be made up and should be documented in the dosing record form. Patients will be instructed to return any unused capsules. The number of tablets/capsules returned by the patient will be counted, documented, and recorded.

6.1.5. Silmitasertib (CX-4945) Dose Modifications

The most common drug related adverse events reported for CX-4945 are predominantly gastrointestinal disorders, including nausea, vomiting and diarrhea. The dose interruption, reduction, and permanent discontinuation for any toxicity are described below. Dose modification instructions provided bellow do not substitute for investigators' medical judgement. Investigators should always manage their patients according to their medical judgement based on the particular clinical circumstances.

Table 3. Silmitasertib (CX-4945) Dose Modification and Management for potential toxicities (attributable to Silmitasertib)

CTCAE 5.0 Grade (attributable to Silmitasertib)	Treatment Modifications
Grade 1	Treat on time. dose reduction is not required
Grade 2	Hold until≤ Grade 1, resume at same dose
Grade 3	Hold until< Grade 2, resume at dose reduced by 1 level (200 mg)
Grade 4	Hold until Grade 2, resume at dose reduced by 1 level (200 mg).
	Permanent discontinuation can be considered by at the
	Investigator's discretion

• **Dose Reduction:** If a dose-response relationship for toxicity is observed, a reduced dose can be given to the subject. Dose adjustments will be allowed based on the toxicity, efficacy evaluation, and clinical judgment by physician.

CONFIDENTIAL Page 31 of 66

- **Dose Interruption:** Refer to Table 3 above. Recovery to acceptable levels must occur to allow Silmitasertib (CX-4945) continuation.
- **Dose Discontinuation:** Treatment with CX-4945 can be discontinued prematurely due to the following reasons:
 - Disease Progression
 - o Respiratory failure requiring invasive mechanical ventilation,
 - Shock (defined by SBP < 90 mm Hg, or Diastolic BP < 60 mm Hg), or
 - Multiple organ dysfunction/failure
 - Intolerable toxicity most probably attributable to CX-4945.
 - Pregnancy
 - o Significant study therapy non-compliance
 - o If any clinical adverse event (AE), laboratory abnormality, or other medical condition or situation occurs such that continued treatment under the protocol would not be in the best interest of the participant
 - Withdrawal of consent from study treatment or participation

Discontinuation from the study drug does not mean the withdrawal from the study assessments. Subjects who discontinued therapy should remain in the study and continue follow-up for key outcomes. The only reasons for study withdrawal are withdrawal of consent from study participation and loss to follow-up.

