6.3. CONCOMITANT MEDICATION

6.3.1. Premedication - Antiemetic Drugs (Mandatory)

All patients assigned to treatment with CX-4945 (Arm A) will take an oral 5-HT3 antagonist daily, at least 1 hour prior to taking the CX-4945 capsules or a 5-HT3 antagonist transdermal patch at least 24 hours prior to taking the CX-4945 capsules every 7 days. If a patient prefers 5-HT3 antagonist transdermal patch, the patient is expected to apply the patch approximately 24 hours before the day 1. If the patch is missed, the patient will be suggested to taking the oral 5-HT3 antagonist 1 hour before taking CX-4945 on day 1 and continue taking the oral 5-HT3 antagonist for 7 days in order to switch to an antagonist patch.

Medications within the 5-HT3 antagonist class are interchangeable depending on availability and tolerability. Dose(s) of the antiemetic medication, either intensity or frequency can be adjusted as clinically indicated. Patients should receive enough supply to cover the entire treatment.

5-HT₃ antagonist (choose one)

- Dolasetron 100 mg PO daily
- Granisetron 1 mg PO twice daily; the first 1 mg dose should be given up to 1 hour before CX-4945 (with second 1 mg dose 12 hours later) or 3.1 mg/24-h transdermal patch every 7 days
- Ondansetron 8 mg PO twice daily; the first 8 mg dose should be given up to 1 hour before CX-4945 (repeat dose 8 hours after the initial dose)

Management of breakthrough nausea and vomiting should take place as necessary.

6.3.2. Anti-Diarrheal Medication (Recommended):

- All patients assigned to treatment with CX-4945 (Arm A) should be advised to obtain an adequate supply of loperamide (IMODIUM®) with explicit instructions for the management of diarrhea.
- Early diarrhea or abdominal cramps occurring within the first 24 hours is treated with atropine 0.3 1.2 mg IV or SC. Prophylactic atropine may be required for subsequent treatments.

CONFIDENTIAL Page 33 of 66

- Late diarrhea has a median onset of 2 days post-treatment with CX-4945 and must be treated with loperamide (e.g., IMODIUM®). Instruct patient to have loperamide on hand and start treatment at the first poorly formed or loose stool, or earliest onset of more frequent stool than usual:
 - o 4 mg start
 - o then 2 mg every 2 hours until diarrhea-free for 12 hours
 - o may take 4 mg every 4 hours at night

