6.3.3. Electrolyte Abnormalities

Electrolyte abnormalities are common adverse events with Silmitasertib (CX-4945) which may predispose subjects to arrythmias.

- a. Mandatory 5-HT3 antagonist pre-medication may compound this effect. To adequately monitor for this risk, a 24-hour telemetry monitoring for subjects with electrolyte abnormalities may be performed, if clinically indicated.
- b. Use of atropine as an anti-diarrheal medication may also compound this effect. Investigator should consider use of another anti-diarrheal agent for subjects who have persistent diarrhea despite use of loperamide.

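### As printed, Table 3 lets CX-4945 restart at Grade 2 after an attributable Grade 4 toxicity, a looser threshold than for Grade 3 (subject to a check of the source page)

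*Combined protocol and SAP*

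**What the plan says.** Section 6.1.5, Table 3, sets the action by CTCAE grade for toxicity attributed to CX-4945. Grade 1 needs no dose change. Three rows interrupt dosing:

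- The Grade 4 row says "Hold until Grade 2, resume at dose reduced by 1 level (200 mg", with permanent discontinuation as an option for the investigator.
- The row for Grade 3 differs by a sign before the grade: "Hold until< Grade 2, resume at dose reduced by 1 level (200 mg".
- For Grade 2 the instruction is "Hold until≤ Grade 1, resume at same dose".

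The column header gives only the attributable CTCAE 5.0 grade. It does not say whether that means the onset, worst or current grade.

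Three other statements in the section bear on restarting. The Dose Interruption bullet points back to Table 3 and adds "Recovery to acceptable levels must occur to allow Silmitasertib (CX-4945) continuation", without defining an acceptable level. The opening paragraph says "Dose modification instructions provided bellow do not substitute for" the investigator's own judgement. The Dose Reduction bullet says "Dose adjustments will be allowed based on the toxicity, efficacy evaluation, and clinical judgment by physician". I found no restart grade anywhere else in the document.

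**The concern.** A restart rule should be no more permissive after a worse event. As printed, a patient whose attributable toxicity peaked at Grade 3 must wait for Grade 1 before resuming, while one whose toxicity peaked at Grade 4 may resume at Grade 2. Both resume with the same 200 mg reduction.

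Safety and tolerability are the primary objective (Section 3), and Table 3 is the only restart rule after a life-threatening event. Enrolment is at two locations, so investigators could apply an unclear threshold differently. Treatment-emergent events are also to be tabulated by their impact on study treatment, including drug interruption (Section 9.8.4.3).

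Section 6.3.3 offers one setting where the threshold could matter: "Electrolyte abnormalities are common adverse events with Silmitasertib (CX-4945) which may predispose subjects to arrythmias". It adds that the compulsory 5-HT3 antagonist may worsen this risk. Restarting CX-4945 would restart that premedication too. Telemetry is optional, and the only scheduled ECG after screening is at Day 14 (Section 8.2.1.5).

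**Working it through.** The plan states no figure on this point, so the main check is a comparison of the rows.

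**Step 1: restart grades as printed.** CTCAE grades are whole numbers, so below Grade 2 and at most Grade 1 mean the same. Writing 0 for full resolution:

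| Row | Printed threshold | Grades at which drug may restart | Dose on restart |
|---|---|---|---|
| Grade 2 | ≤ Grade 1 | 0, 1 | same |
| Grade 3 | < Grade 2 | 0, 1 | reduced by 200 mg |
| Grade 4 | Grade 2, no sign | 0, 1, 2 | reduced by 200 mg |

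The rows differ only at Grade 2.

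**Step 2: which row governs a Grade 4 event now at Grade 2?** The header does not say, so take both readings.

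- *Rows follow the current grade.* The Grade 2 row would then apply and say hold. It would also say to resume at the same dose. Every Grade 3 or Grade 4 event that resolves through Grade 2 would lose its 200 mg reduction, and those two rows would have no lasting effect.
- *Rows follow the triggering event.* Only the Grade 4 row applies, and every row keeps its effect. This is the natural reading. No other row contradicts the Grade 4 row, but two anomalies remain: its threshold is looser than the Grade 3 threshold, and drug restarts at a grade which, arising by itself, would call for a hold.

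**Step 3: could a sign have been lost?** The Grade 2 and Grade 3 rows each carry a sign where the Grade 4 row has none. The text reviewed was converted from PDF.

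| Source page shows | Grade 4 restart grades | Result |
|---|---|---|
| < Grade 2 | 0, 1 | no anomaly |
| ≤ Grade 2 | 0, 1, 2 | anomaly stands |
| no sign | 0, 1, 2 | anomaly stands |

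Characters do appear to be missing elsewhere. Section 6.3.2 reads "treated with atropine 0.3 1.2 mg IV or SC", apparently without a range dash, and footnote 11 of Table 1 has no marker in the table. On the other side, the signs in the two adjacent rows survived, as did the less-than signs in the shock definition of the same section.

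**Step 4: how many patients could be affected?** Section 9.3 randomises 40 patients 1:1, so Arm A has about 40/2 = 20. The documents give no Grade 4 rate, so both inputs below are assumptions: p is the proportion of Arm A with an attributable Grade 4 event, and q is the fraction of those in whom the row changes a decision (the event reaches Grade 2 with treatment days left, and the investigator restarts then).

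- Chance of at least one Grade 4 event, an upper bound on reach: 1 − (1 − p)^20.
- Chance that at least one patient's restart is affected: 1 − (1 − pq)^20.
- Expected number affected: 20pq.

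| p | Upper bound | At least one affected, q = 0.25 | At least one affected, q = 0.50 | Expected, q = 0.25 to 0.50 |
|---|---|---|---|---|
| 0.02 | 33% | 10% | 18% | 0.1 to 0.2 |
| 0.05 | 64% | 22% | 40% | 0.25 to 0.5 |
| 0.10 | 88% | 40% | 64% | 0.5 to 1.0 |

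The table shows only how reach would vary with p and q. It is not evidence that such events will occur.

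**The case against.** **The missing sign may come from the PDF conversion.** This stands as a limit on confidence. A lost less-than sign would mean there is nothing to correct. A loss cannot simply be presumed, though, and a lost ≤ would leave the problem in place.

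**The rows do not contradict each other.** This also stands. A reader might infer that Table 3 tells the investigator both to resume and to hold for a Grade 4 toxicity that has fallen to Grade 2. The documents do not support that. It needs the rows to follow the current grade, which the table never states and which would cancel the dose reductions for Grades 3 and 4. Read by triggering event, the Grade 4 row alone applies.

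**Safeguards limit the effect.** The investigator's judgement takes precedence, permanent discontinuation is named in the Grade 4 row, and treatment may be stopped for intolerable toxicity or whenever continuing is not in the patient's interest. Life-threatening events are reported to the sponsor immediately (Section 8.3.5), and a monitoring committee reviews adverse event listings (Section 9.9). These reduce the consequence, but none supplies a restart grade. Section 7.3 asks investigators to contact the medical monitor before discontinuing treatment; I found no matching step before restarting after Grade 4.

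**The electrolyte example is only one setting.** Electrolytes are measured on Days 1, 4, 8, 11 and 14 (Section 1.3), and extra laboratory tests are allowed at any time (Section 8.2.1.4). Section 6.1.5 says the common drug-related events are mainly gastrointestinal. The documents do not say how often electrolyte abnormalities reach Grade 4. The example shows why a clear threshold is useful, not that harm is likely.

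**Conclusion.** The point holds as an internal inconsistency in the restart thresholds. As printed, the Grade 4 row allows CX-4945 to resume at Grade 2. That is looser than the Grade 3 row, and Grade 2 is itself a grade that triggers a hold. Confidence is low to medium, because a less-than sign on the source page would remove the point entirely.

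Reach is low. Section 2.4 describes most adverse events as mild to moderate, and Arm A has about 20 patients. Under the assumed rates the expected number affected runs from 0.1 to 1.0, but no figure in the documents supports any particular value in that range. No efficacy analysis rule changes. The case for acting is that the rule governs restarting after a life-threatening toxicity in a trial whose primary objective is safety, and that the correction is small.

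**What to change.** 1. Check the Grade 4 row of Table 3 on the source page. If it shows a less-than sign before Grade 2, the threshold needs no change.
2. Otherwise, require Grade 1 or lower before resuming in the Grade 4 row. Keep the one-level (200 mg) reduction and the investigator's option to discontinue permanently.
3. Write the Grade 3 threshold as ≤ Grade 1. The meaning is the same, and the three hold rows then match.
4. State that rows apply to the worst grade of the triggering event. Without this, a reader could still apply the Grade 2 row to a resolving Grade 3 or 4 event and restart at the full dose.

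This is one row of one table, matching wording in another row, and one added sentence, by clarification letter or with the next amendment. Writing ≤ Grade 1 does no harm if a less-than sign was lost, since the two are equivalent.

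The clinical cost is a slightly longer hold for very few Arm A patients. Planned doses are 2 per day × 14 days = 28 (Section 6.1.3), and missed doses are not replaced (Section 6.1.4). One, two or three extra hold days therefore cost 2/28 = 7.1%, 4/28 = 14.3% or 6/28 = 21.4% of planned doses for the patient concerned.

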6.2. INVESTIGATIONAL PRODUCT SUPPLIES, STORAGE AND ACCOUNTABILITY

6.2.1. Investigational Product Supplies

CX-4945 will be supplied by Senhwa Biosciences. Study center will receive CX-4945 prior to enrollment of the first patient. The clinical site pharmacy/qualified staff member will dispense the supplies to the patients enrolled to the treatment Arm A in quantities appropriate for the study visit schedule. Any unused product or waste material should be disposed of in accordance with local requirements.

6.2.2. Formulation, Appearance and Packaging

CX-4945-PIC has been manufactured as neat API powder in hard shell gelatin capsules (Capsugel) in a dose strength of 200 mg capsules (Powder in Capsule (PIC) formulation), for immediate release, oral administration. There are no excipients used for PIC formulation.

Clinical trial material supply of CX-4945-PIC for oral administration are supplied as 200 mg strength in size 1, opaque blue capsules, contained in 60 cc, wide mouth, white, high-density

CONFIDENTIAL Page 32 of 66

polyethylene (HDPE) bottles. Each bottle contains fifteen capsules with one (1 gram), white plastic PTC-0005 desiccant pod, and is induction heat sealed.

6.2.3. Product Storage and Stability

CX-4945 clinical trial material should be stored in the container provided, between 15°C-30°C (59°F-86°F), and should be protected from moisture, freezing, and bright light.

6.3. CONCOMITANT MEDICATION

6.3.1. Premedication - Antiemetic Drugs (Mandatory)

All patients assigned to treatment with CX-4945 (Arm A) will take an oral 5-HT3 antagonist daily, at least 1 hour prior to taking the CX-4945 capsules or a 5-HT3 antagonist transdermal patch at least 24 hours prior to taking the CX-4945 capsules every 7 days. If a patient prefers 5-HT3 antagonist transdermal patch, the patient is expected to apply the patch approximately 24 hours before the day 1. If the patch is missed, the patient will be suggested to taking the oral 5-HT3 antagonist 1 hour before taking CX-4945 on day 1 and continue taking the oral 5-HT3 antagonist for 7 days in order to switch to an antagonist patch.

Medications within the 5-HT3 antagonist class are interchangeable depending on availability and tolerability. Dose(s) of the antiemetic medication, either intensity or frequency can be adjusted as clinically indicated. Patients should receive enough supply to cover the entire treatment.

5-HT₃ antagonist (choose one)

- Dolasetron 100 mg PO daily
- Granisetron 1 mg PO twice daily; the first 1 mg dose should be given up to 1 hour before CX-4945 (with second 1 mg dose 12 hours later) or 3.1 mg/24-h transdermal patch every 7 days
- Ondansetron 8 mg PO twice daily; the first 8 mg dose should be given up to 1 hour before CX-4945 (repeat dose 8 hours after the initial dose)

Management of breakthrough nausea and vomiting should take place as necessary.

6.3.2. Anti-Diarrheal Medication (Recommended):

- All patients assigned to treatment with CX-4945 (Arm A) should be advised to obtain an adequate supply of loperamide (IMODIUM®) with explicit instructions for the management of diarrhea.
- Early diarrhea or abdominal cramps occurring within the first 24 hours is treated with atropine 0.3 1.2 mg IV or SC. Prophylactic atropine may be required for subsequent treatments.

CONFIDENTIAL Page 33 of 66

- Late diarrhea has a median onset of 2 days post-treatment with CX-4945 and must be treated with loperamide (e.g., IMODIUM®). Instruct patient to have loperamide on hand and start treatment at the first poorly formed or loose stool, or earliest onset of more frequent stool than usual:
 - o 4 mg start
 - o then 2 mg every 2 hours until diarrhea-free for 12 hours
 - o may take 4 mg every 4 hours at night

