6.4. SILMITASERTIB (CX-4945) DRUG INTERACTION

6.4.1. Effect of CX-4945 in Human Liver Microsomes

The absorption, distribution, metabolism, and excretion (ADME) properties of CX-4945 have been evaluated in in vivo to support nonclinical safety evaluations and to assess the potential relevance to humans. CX-4945 was tested in a non-GLP in vitro ADME-TOX in human liver microsomes with the following seven key CYP450 isoenzymes: CYP1A2, CYP2B6, CYP2C8, CYP2C9, CYP2C19, CYP2D6 and CYP3A4. CX-4945 did not show significant inhibition or induction of any CYP isoenzymes tested in this study (for all isozymes more than 80 percent remained after 60 minutes and it was not possible to calculate a specific half-life).

The result suggests that CX 4945 does not inhibit or induce these seven CYP450 isozymes, and can therefore be safely co-administered with drugs that are metabolized via this pathway.

Antiemetic drugs (5-HT3 antagonist) are required and anti-diarrheal drugs are recommended for concomitant use in the treatment group A for management of possible GI toxicities. CYP3A4 is the predominant enzyme pathway for ondandestron and granisteron metabolism. Loperamide is metabolized by the cytochrome P450 (CYP) system and is a substrate for the CYP3A4 isoenzyme. Approximately 200 subjects have been treated with CX-4945 in Phase I/II clinical trials to date and approximately 115 subjects received required and /or recommended concomitant treatment with

CONFIDENTIAL Page 34 of 66

antiemetic and antidiarrheal drugs. CX-4945 was safely co-administered with concomitant medications with no drug-drug interaction (DDI) observed.

Because complete CX-4945 metabolism information is not available at this point and treatment with 5-HT3 antagonist and anti-diarrheal drugs is planned for treatment arm A, current use or anticipated need for drugs that are known strong inhibitors or inducers of major CYP enzymes should be avoided from Day 1 through Day 14. If the replacement is not possible, then patients taking strong inhibitors or inducers of major CYP enzymes should not be enrolled to the study (exclusion criterion #6).

CONFIDENTIAL Page 35 of 66

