8.3.1. Definitions of Adverse Event (AE)

An adverse event (AE) is defined as any unfavorable or unintended sign, symptom, or disease that occurs or is reported by the patient to have occurred, or a worsening of a pre-existing condition. An adverse event may or may not be related to the study treatment.

AEs will be elicited through direct questioning and subject reports. Any abnormality in physical examination findings or laboratory results that the investigator believes is clinically significant (CS) to the research subject and that occurred after initiation of the first study treatment will be reported as AEs. Abnormal findings that are NOT clinically significant should not be recorded as an AE.

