9.8.4.3. Safety Summaries

Adverse Events

Adverse events will be coded using the most recent version of Medical Dictionary for Regulatory Activities (MedDRA). Treatment Emergent AE's (TEAE) are defined as events with an onset on or after the first treatment. TEAEs will be summarized by treatment group, System Organ Class, and preferred term. The following TEAE summaries will be provided:

- Overall (i.e., regardless of severity or relationship to treatment);
- By intensity (mild, moderate, severe, life threatening or death);
- By causality (definitely, probably, possibly, remotely or unrelated);
- By impact on study treatment (dose increased, dose not changed, dose rate reduced, dose reduced, drug interrupted, drug withdrawn, not applicable, or unknown).

In addition, separate summaries of serious adverse events, and adverse events resulting in discontinuation of study treatment will be presented.

Clinical Laboratory Data

All laboratory values will be listed. Laboratory measurements will also be summarized and presented by treatment group and time point.

CONFIDENTIAL Page 52 of 66

ECG

All ECG values will be listed. ECG measurements will also be summarized and presented by treatment group and time point.

Vital Signs

All vital sign findings will be listed and/or summarized.

Physical Examination

All physical examination findings will be listed and/or summarized.

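### Only Arm A is briefed to notice and act on the first loose stool, and AE questioning has no set content, so the by-arm table of mild GI events is at risk of differential ascertainment

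*Combined protocol and SAP*

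**What the plan says.** **Arm A only.** Section 6.3.1 schedules antiemetic premedication: "All patients assigned to treatment with CX-4945 (Arm A) will take an oral 5-HT3 antagonist daily", with a transdermal patch as the alternative. Under Section 6.3.2, Arm A patients "should be advised to obtain an adequate supply of loperamide (IMODIUM®) with explicit instructions for the management of diarrhea". For later diarrhea the instruction is: "Instruct patient to have loperamide on hand and start treatment at the first poorly formed or loose stool", or at the earliest rise in stool frequency. Section 6.4.1 confirms where these measures apply: "anti-diarrheal drugs are recommended for concomitant use in the treatment group A for management of possible GI toxicities". No corresponding briefing for Arm B appears in the protocol.

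**Both arms.** Section 8.3.1 states: "AEs will be elicited through direct questioning and subject reports". It gives no question list, stool count or recall period. Section 9.5 makes the trial open label.

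**Role of these data.** Section 3 makes AEs from randomization to Day 60, by type, frequency, severity and other features, the primary endpoint. Section 6.1.5 describes the commonest drug-related events as predominantly "gastrointestinal disorders, including nausea, vomiting and diarrhea". Section 9.8.4.3 states: "TEAEs will be summarized by treatment group, System Organ Class, and preferred term".

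**The concern.** The event most expected with CX-4945 is also the one that Arm A patients are specifically taught to look for. An Arm A patient who has been told to start loperamide at the first loose stool has a reason to notice it and mention it. An Arm B patient with the same stool has no such prompt. The person asking knows the arm. Table 3 in Section 6.1.5 adds a further reason to look for and grade GI events in Arm A, because study-drug dosing depends on the grade of attributable toxicity. After discharge, follow-up may be by telephone, text or email (Table 1, footnotes 16 and 17), where a mild symptom is recorded only if it is asked about or volunteered.

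The control column is the only randomized background against which GI events in Arm A can be read. If mild diarrhea is recorded less completely in Arm B, that background is too low. Events that were never recorded cannot be recovered at analysis.

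**Working it through.** There is no figure in the plan to reproduce. Section 9.3 fixes 40 patients, 1:1, on clinical judgment, and no GI rate or recording rate is given. All rates below are assumptions, chosen to show a range.

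**Inputs**
- n = 20 per arm (Section 9.3: 40 patients, 1:1).
- True proportion with a mild GI event, equal in both arms: p = 0.20 to 0.40 (assumed).
- Proportion of those recorded: Arm A, sA = 0.95 to 1.00; Arm B, sB = 0.50 to 0.80 (assumed).

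**Step 1. Recording alone.** Spurious difference = p × (sA − sB).
- Smallest gap: 0.95 − 0.80 = 0.15. Largest gap: 1.00 − 0.50 = 0.50.

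| p | Gap 0.15 | Patients of 20 | Gap 0.50 | Patients of 20 |
|---|---|---|---|---|
| 0.20 | 3.0 points | 0.6 | 10 points | 2.0 |
| 0.30 | 4.5 points | 0.9 | 15 points | 3.0 |
| 0.40 | 6.0 points | 1.2 | 20 points | 4.0 |

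The range is 3 to 20 points. With sA = sB the difference is 0 at every p.

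**Step 2. Medication acting the other way.** Assume 30% of patients would have an event on CX-4945 without GI medication and 20% in Arm B, so the drug alone adds 10 points. Assume GI medication removes 40% of events in Arm A.
- True difference between regimens: 0.30 × 0.60 − 0.20 = 0.18 − 0.20 = −2 points.
- Observed, 90% recorded in both arms: 0.18 × 0.90 − 0.20 × 0.90 = 0.162 − 0.180 = −1.8 points.
- Observed, 90% in A and 60% in B: 0.162 − 0.20 × 0.60 = 0.162 − 0.120 = +4.2 points.

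On these assumptions unequal recording reverses the sign. Other values would not, so neither direction nor size can be set from the documents. The −2 points is the true result for the regimen; only the shift from −1.8 to +4.2 is a recording effect.

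**Step 3. Comparison with chance.** 95% half-width = 1.96 × √[pA(1 − pA)/20 + pB(1 − pB)/20], at the observed rates for the two extremes of Step 1.
- 0.19 vs 0.16: 1.96 × √(0.1539/20 + 0.1344/20) = 23.5 points, against a spurious 3.
- 0.40 vs 0.20: 1.96 × √(0.24/20 + 0.16/20) = 27.7 points, against a spurious 20.

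Chance variation exceeds the recording effect at both extremes.

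**The case against.** The strongest reply is that ascertainment is not left to the patient. Direct questioning is prescribed for everyone, and Table 1 collects AEs at the same visits in both arms. Patients are enrolled in hospital, clinical status is assessed daily to Day 28, and Section 13.1 makes the medical record the primary source. The AE form is not among the documents and may carry a GI prompt. This lowers the likely size of the gap. It does not remove the gap, because the protocol leaves the content of the questioning open, the questioner knows the arm, and the one-sided briefing remains.

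A second reply is that the analysis is descriptive. Section 9.8.4 plans no inferential statistics for study outcomes, the primary objective names no comparison with control, and causality is judged event by event (Section 8.3.3.2). The half-widths in Step 3 also exceed the spurious differences. This stands as a reason to treat the point as modest. But imprecision does not cancel a systematic difference, and counts by arm will still be read side by side.

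A reader might go further and infer that premedication biases the severity rows. The documents do not support that. Less nausea or milder diarrhea under scheduled GI medication is a real result of the Arm A regimen, not a recording error. Nor is Arm B barred from GI drugs: Section 6.1.1 leaves supportive care to the investigator, so they are unscheduled there rather than withheld.

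**Conclusion.** The point holds as a risk of differential ascertainment of mild GI events, chiefly diarrhea, within the primary endpoint. The one-sided briefing, the open-label design and the unspecified questioning are all in the text. The size is not. The 3 to 20 points (0.6 to 4 of 20 patients) rests on assumed true and recording rates, and is zero if recording is equal.

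A reader might conclude that the GI comparison is biased against CX-4945 and that the excess is overstated. That does not follow. Scheduled antiemetic and anti-diarrheal use in Arm A works in the opposite direction, so the net direction is unknown. What remains is a weakness that is cheap to remove, in a small descriptive comparison.

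**What to change.** - **Section 8.3.1:** in both arms, at every visit where Table 1 already collects AEs, ask the same short list: nausea, vomiting, loose stools with number per day, and abdominal cramps, each with worst grade since last contact. Use the same wording in person and by telephone. Include a pre-treatment status on Day 1. Allocation is already known by then, because randomization precedes the other Day 1 assessments, but existing symptoms would at least be on record in both arms.
- **Section 9.8.4.3:** base the descriptive by-arm GI table on these answers. Place antiemetic, loperamide and atropine use by arm beside it. Section 9.8.3 already summarizes concomitant medication by treatment group, so only the placement is new. Note on the table that Table 1 collects concomitant medication to Day 28 and AEs to Day 60.
- **Label** the table as a comparison of regimens: CX-4945 plus GI medication versus SOC.

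The clinical instructions in Section 6.3 are left unchanged. The cost is one short CRF page and one table layout, with no new visit and no change in sample size. The downside is that recorded rates of mild GI events will rise in both arms.
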